mHealth-Assisted Conditional Cash Transfers to Improve Timeliness of Vaccinations (MINT)

ClinicalTrials.gov ID NCT03252288

Do mobile phone-based reminders and conditional financial transfers improve the timeliness of childhood vaccinations in Tanzania? Study protocol

Globally, childhood vaccinations are estimated to prevent 2.5 million deaths annually. [1] Yet, 19.7 million children under the age of 1 year have missed receiving basic vaccinations. [1] The majority of un- or under-vaccinated children reside in low- and middle-income countries (LMICs), with those from rural, remote, and poorer households being disproportionately less likely to receive all recommended vaccines in their first year of life. [1-3] In Tanzania, for example, 1 in 4 children has not received all recommended vaccines in the first year of life, compared to 1 in 10 globally. [4, 5] Significant regional variation in vaccination coverage has been reported in Tanzania, with several regions failing to meet the 80% coverage target set forth in the Global Vaccine Action Plan. [5-7] Furthermore, numerous reports indicate low timeliness of vaccinations in LMICs, including in Tanzania. [8-10] In a study in rural Tanzania, vaccination delays were reported in 69% of children for the third dose of the diphtheria-pertussis-tetanus (DPT) vaccine, and in 46% of children for the measles-containing vaccine (MCV). [10] In the quest for universal immunization, innovative strategies are needed to improve vaccination coverage for the “last mile”, and to reduce vaccination delays that leave children susceptible to unnecessary morbidity and mortality from vaccine-preventable infections.

Barriers to timely immunization are multifaceted and include immunization system constraints (e.g., vaccine stock-outs, limited availability of health care providers), poor access to health facilities (e.g., transport cost, opportunity cost), lack of information (e.g., about the vaccination schedule or community mobilizations), and negative parental attitudes and inadequate knowledge (e.g., lack of trust in vaccinators, poor knowledge of vaccination benefits, fear of vaccination side effects). [3, 11, 12] In recent years, many groups have leveraged the global pervasiveness of mobile phones for alleviating some of these barriers in order to improve vaccination coverage and timeliness in LMICs. [13, 14] Implementations of mobile phone-based (“mHealth”) strategies in the context of vaccinations include birth notification and newborn surveillance for early identification of children eligible for vaccination services; [15-17] development of digital vaccination registries to longitudinally track the vaccination status of children and rapidly identify those who are un- or under-vaccinated; [17-23] use of text messages (SMS) or simple voice communication to deliver health promotion messages and reminders about upcoming vaccination appointments; [17, 24-26] delivery of incentives for timely vaccinations; [27-29] digital aids to assist vaccinators in counseling parents, [23] for work planning and scheduling, [17, 18, 23] or for vaccine stock management; [30] and curation of

performance indicators at the regional and national levels. [31] Despite these numerous instantiations, the evidence-base on the efficacy of mHealth strategies for improving childhood vaccination coverage and timeliness is limited, with the need for rigorous evaluations identified in several systematic reviews. [14, 32, 33]

With support from the National Immunization and Vaccines Development (IVD) program of the Tanzanian National Ministry of Health, Community Development, Gender, Elderly and Children, we are evaluating the efficacy of mobile phone-based vaccination reminders and incentives in the form of conditional financial transfers (CFTs) for offsetting demand-side barriers to timely vaccination. Per the recently released WHO classification of digital health interventions, the two key interventions in this study correspond to 1.1 Targeted client communication (specifically, 1.1.3 Transmit targeted alerts and reminders to clients), and 1.7 Client financial transactions (specifically, 1.7.3 Transmit or manage incentives to clients for health services.) [34] Our hypothesis is that reminders and incentives will increase timeliness of vaccinations relative to the status quo. The design and protocol of the evaluation are described below.

Methods/Design

Study aim

The aim of the study is to assess the efficacy of (1) mobile phone-based reminders, and (2) mobile phone-based reminders combined with incentives in the form of CFTs, for improving vaccination timeliness among children at 6, 10 and 14 weeks after birth, compared to the standard of care.

Outcome measures

The recommended schedule for vaccinations by age 1 year is presented in **Table 1**. The primary study outcome is whether or not a child received an on-time vaccination; the outcome is measured for vaccinations scheduled at 6, 10 and 14 weeks after birth. Secondary outcomes include vaccination coverage, in aggregate and for each of the vaccinations due at 6, 10 and 14 weeks after birth. Timeliness is defined as vaccination within 28 days of the scheduled vaccination due date. Coverage is defined as the percentage of children vaccinated.

Study design

The study design represents a quasi-randomized controlled trial that includes three phases, each corresponding to one study arm: 1) standard of care (no reminders or incentives); 2) mobile phone-based reminders; and 3) mobile phone-based reminders combined with incentives in the form of CFTs. Arm 1 serves as the control arm; arms 2 and 3 are intervention arms. The trial is enfolded by base- and end-line assessments (**Figure 1**).

Assignment to study arms and transitions between arms

Assignment to study arms is implemented at the level of the vaccination event, with all vaccination events scheduled during a phase assigned to the corresponding arm. T_1 , the beginning of Phase 1, denotes the time of participants' enrollment into the control arm. At time T_2 , the beginning of Phase 2, all participants are rolled over to the arm with reminders; at time T_3 , the beginning of Phase 3, all participants are rolled over to the arm with reminders combined with incentives. While T_2 and T_3 denote fixed points in calendar time, variation in delivery dates across participants results in between- and within-individual variation in the assignment of vaccination events across the three arms. **Table 2** shows all possible combinations of vaccination event assignments to study arms at the level of the participant. With dates of birth exogenously determining children's vaccination schedules, shifts in T_2 and T_3 directly affect the number of vaccination events that may be observed in each study phase. Based on the distributions of expected delivery and vaccination due dates, T_2 and T_3 are chosen such that the expected number of vaccination events is approximately equal across the three arms. With T_2 and T_3 being random in relation to mothers' delivery dates, and thus children's vaccination schedules, the assignment of vaccination events across arms may be considered quasi-random. Loss to follow-up and other reasons for non-delivery of vaccination reminders result in exposure indistinguishable from the control condition.

The assignment to study arms based on scheduled vaccination dates, and the simultaneous transition of all participants between study arms, address concerns that the individual randomization into, and co-existence of, incentive and non-incentive arms are not considered viable within closely-knit communities. While cluster randomization was considered as an alternative approach, the heterogeneity of clusters suggests that this approach would confound the effects of settings with the effects of reminders and incentives.

Study setting

The study is conducted in two adjacent districts, one urban district (Mtwara Municipality) and one rural district (Mtwara District Council), in Mtwara Region in Southeastern Tanzania. In 2017, Mtwara Municipality had an estimated population of 115,132; Mtwara District Council had an estimated population of 130,757.[35] Owing to logistical considerations, the study area in the rural district is limited to a 30 kilometer (km) radius around the urban district.

Study participants

Eligible study participants are women, ages 16 or older, who are in the third trimester of pregnancy and have access to a mobile phone. The target enrollment is 400 women.

Recruitment

Participants are recruited from at least 4 urban and at least 8 rural health facilities and the surrounding communities. Eligible health facilities regularly provide childhood vaccinations. A combination of purposive and snowball sampling strategies is used for recruitment as follows: Eligible women presenting for antenatal care at participating facilities are approached by trained study personnel and offered enrollment in the study. To minimize biases from facility-based enrollment, participating women and local community leaders (*balozis*) are asked to identify other pregnant women in their community, who, if eligible, are also offered enrollment in the study.

Enrollment and informed consent

All individuals contacted for participation in the study are informed of the study purpose and procedures, as well as risks and benefits, during the informed consent process by study staff. Women are approached in person and are provided study information orally and in writing using an informed consent script in Kiswahili. Only consenting women are included in the study. Some women may access mobile phones via relatives, friends, or other designees: these persons are considered authorized agents for the purpose of this study. Authorized agents are not considered research subjects and, thus, are not independently consented. By designating authorized agents, participating women are considered to be providing implied consent for these agents to receive information on their behalf.

Since the study includes participants ages 16 years and older, the Institutional Review Board (IRB) granted a waiver of parental consent for pregnant women ages 16 and 17 years old. Tanzanian national policy indicates that adolescents under age 18 who are sexually active are considered “mature minors”, have the right to access reproductive health services without parental or spousal consent, and can make associated medical decisions on their own behalf. [36] Given that sexually active adolescents have this “adult” right to medical decision-making, it was determined that pregnant adolescents ages 16 and 17 years are also able to consent to research participation for themselves without parental or spousal consent.

No blinding

The nature of the interventions, mobile phone-based reminders and incentives in the form of CFTs, precludes blinding of study participants.

Intervention components and implementation

For the delivery of the study interventions, we developed an mHealth system comprising the following components:

Scheduling system: Upon enrollment, a participant’s name, contact information, and EDD are stored in a database, and participants are added to a process queue. For each participant, the process awaits inputs (e.g., date of birth of the child, vaccination dates) and executes tasks according to a pre-specified schedule. Tasks include sending reminder SMS, tracking SMS delivery, and alerting study staff to call participants when follow-up action is required. When event-related inputs (e.g. dates of completed or rescheduled vaccinations) are received by the system, the database and the schedule of tasks are updated. For example, a delay in one vaccination shifts the remaining schedule by the length of the delay.

USSD notification system: Participants can notify the scheduling system of events (e.g., birth of child, vaccinations received) using an Unstructured Supplementary Service Data (USSD) dialog. USSD dialogs, which can be accessed free of charge by dialing a short code from any mobile phone, allow for a two-way exchange of data. In this case, the USSD dialog is implemented analogously to a short survey. Participants are guided through text-based menus which prompt them for information related to the event they are reporting. The information is passed to the scheduling system, which updates the schedule of upcoming tasks.

Mobile phone reminder system: Participants in Arms 2 and 3 receive reminders for upcoming vaccination appointments 1 week and 1 day before the vaccination due date. No reminders are associated with the EDD or the vaccination due at birth. Reminders are issued in the form of text messages to the mobile phone numbers of study participants or their designees. Prior to study implementation, messages were tested for comprehension using a structured template, and revised based on feedback received. The timing of messages is based on findings from a cross-sectional survey of 134 Tanzanian mothers of children ages 12-23 months. In that survey, 54% of women who indicated any mobile phone use wanted to receive reminders one week before the due date, 40% one day before the due date, and 6% on the due date. Data on comprehension are collected in the end-line survey to inform future implementations.

Incentive disbursement system: For each timely vaccination for which a reminder with an incentive offer was sent to a mobile phone, a payment in the form of a mobile phone airtime recharge voucher code (worth either TSH 1000 or TSH 2000) is sent to a mobile phone number specified by the participant. The two-tiered incentive amount, which was chosen ad hoc by the study team as appropriate to 'nudge' participants toward timely vaccinations without significantly changing their economic incentives, [37] is conditional upon the timing of vaccination (see below).

Technical implementation: The scheduling and sending of SMS messages and incentives is implemented via a custom-built task scheduling, execution, and event tracking application called mParis ("mobile phone assisted reminder and incentive system"). mParis, which was developed for another NIH-funded study (R01MH106388), is built using Flowable, a flexible, open source, Java-based, workflow engine (<https://www.flowable.org>). [38] The system is based at the Kilimanjaro Clinical Research Institute, in Moshi, Tanzania.

Study activities

Key events and related study activities are summarized in **Figure 1** and **Table 3**.

Women providing informed consent are enrolled in the study. At the time of enrollment, a baseline survey is conducted with all participants to assess socio-demographic characteristics, mobile phone ownership and use, reproductive history, EDD for the current pregnancy, and vaccination knowledge, history of vaccinations in a prior child, if applicable, and previously experienced or anticipated barriers to vaccinations. Mobile phone numbers are obtained for mothers and any authorized agents. Surveys are implemented electronically on tablet devices

and conducted by study staff at health facilities, participants' homes, or other mutually agreed-upon locations.

Toward the end of Phase 1, all women are contacted by phone to ascertain birth dates and outcomes, and information on past and scheduled vaccinations. The information is used to generate child-specific vaccination schedules. In Phases 2 and 3, reminder messages are sent to registered mobile phone numbers 1 week and 1 day prior to each scheduled vaccination, and, if no vaccination confirmation is received, 2 weeks after the vaccination due date. Uniquely numbered cards, given to participants at each completed or rescheduled vaccination, allow participants to report vaccination dates via the USSD system. When no vaccination report is received via the USSD system, SMS, or phone calls from participants, study staff contact the participant by phone to verify whether and when a vaccination was received, and ascertain the due date for the next vaccination, if applicable. Recorded vaccination dates are used to iteratively update vaccination schedules and to re-schedule reminders.

During Phase 3, reminder messages offer an incentive for each timely vaccination. The full incentive amount (TSH 2000; approximately \$0.90) is paid when a vaccination is received within 2 weeks (14 days) of the due date; half the incentive is paid if the vaccination is completed more than 2 weeks but within 4 weeks (28 days) after the vaccination due date. Incentive amounts are paid if the mother, despite going to the health facility as reminded, is asked to return for a vaccination at a later date. Payments for timely vaccinations are made via an SMS message that includes a network-specific mobile phone airtime recharge voucher code and is sent to a phone number specified by the mother. An in-person end-line survey, conducted 12 months after enrollment, assesses barriers to vaccinations, receipt and acceptability of reminders (Arms 2 and 3) and incentives (Arm 3), and records vaccination dates from participants' government-issued vaccination cards, allowing for comparisons with the data recorded in the mHealth system.

Data management

Password protected tablet devices are used to collect survey data from participants. Data transfer agreements (DTAs), signed by all participating institutions, guide the secure sharing of data between Tanzania and foreign collaborators. To ensure confidentiality, identifying information are collected, transferred, and stored separately from survey data. On-site study monitoring, performed by the Principal Investigators or their designees, is used to verify

compliance with human subjects and other research regulations and guidelines, assess adherence to the study protocol, and confirm the quality and accuracy of information collected and entered into the study database. All collaborators have access to the final data.

Statistical analysis

For each participant, outcomes are observed at three time points (corresponding to timely vaccinations at 6, 10 and 14 weeks, respectively). The probability of timely vaccinations and its association with reminders and incentives will be analyzed using a random effects logistic regression model. The outcome variable is 1 if the vaccination was received on-time, and 0 if early, delayed, or not received at all. The primary covariates of interest are indicator variables for the receipt of reminders only (“*reminder*”) and the receipt of reminders with an incentive offer (“*reminder+incentive*”). For arm 1 the value of both covariates is 0 for all three time points. For outcomes in arm 2, the value for *reminder* (and for arm 3 the value for *reminder+incentive*) is 1 if the mHealth system confirmed delivery of the reminder, and 0 for all other observations. Additional covariates (e.g. mother’s education, rural vs. urban residence, recruitment from health facilities vs. the community) will control for differences in participant characteristics between study arms and their association with vaccination timeliness. Interactions of *reminder* and *reminder+incentive* with these covariates describe systematic variation in the effects of reminders and incentives on vaccination timeliness. Models will control for the number of phone-based contacts prior to or within the timeliness window for any given vaccination, and standard errors will be adjusted to account for clustering at the level of the health facility catchment area.

Statistical power

Across 400 participants we expect up to 1,200 data points on vaccination timeliness. Assuming (a) that these data points are distributed equally across the 3 study arms (standard of care; reminders only; reminders and incentive); (b) a 10% attrition rate; (c) equal cluster sizes of 10 women per health facility catchment area, with an intra-cluster correlation of 0.02; (d) 3 observations per child, with a within-child correlation of 0.2; (e) a baseline rate of vaccination timeliness of 65% in the control condition; and (f) a 10 (15) percentage point difference associated with reminders (reminders and incentives), the power ($\alpha=.05$, 2-tailed) to detect such difference is 72% (98%).

Dissemination

Results will be shared with stakeholders at the regional and national levels, presented at national and international conferences, and published in high impact academic journals.

Data sharing

Efforts will be made to develop a data repository for the storage of de-identified study data. Investigators wishing to use study data to answer new research questions may submit data analysis concept proposals for consideration by the Principal Investigators. The Principal Investigators will review the proposal and will provide those submitting scientifically rigorous and promising proposals access to the data repository to address their research questions.

Discussion

This study examines the efficacy of mobile phone-based reminders and incentives in the form of conditional financial transfers for offsetting demand-side barriers to timely childhood vaccinations in Tanzania. Our implementation strategy has several unique components, including the use of a USSD-based birth and vaccination event notification system, an adaptive schedule for vaccination reminders which is derived from the date of the preceding event, a tiered incentive system, and the automated disbursement of mobile phone credit for eligible timely vaccinations.

The study is subject to several limitations: First, feasibility considerations limit the study area to include only health facilities and their catchment areas within approximately 30 km of Mtwara municipality. More remote populations may face additional barriers that cannot be evaluated in this study. Second, only women with access to mobile phones are included in the study. To minimize selection bias, women could designate anyone with a mobile phone to be their study contact. However, for women relying on such authorized agents, receipt of messages and payments for timely vaccinations could remain a challenge. Third, reminder schedules and payments for timely vaccinations are based on client-reported birth and vaccination dates. The dependence on client reports may introduce delays, affect schedule accuracy, and motivate inaccurate reporting of vaccination dates. Comprehensive quality control, including automated alerts to study staff for participant follow-up, algorithms that identify inconsistencies in near real time, and an in-person end-line survey with a review of government-issued vaccination cards, will be used to assess and/or mitigate these concerns. Fourth, it is plausible that follow-up phone calls by study staff to ascertain birth outcomes, the timing of past vaccinations, and/or the

timing of the next scheduled vaccination, may themselves function as an intervention. Fifth, temporal changes that coincide with the points of transition between study arms could influence results. Finally, while the primary focus of the study is on demand-side barriers to timely vaccinations, participating health facilities may encounter vaccine stock outs and power outages, resulting in vaccination activities being deferred until vaccine stocks are received or power is restored. We plan to monitor these events along with mHealth system and mobile network metrics (e.g., message transmission errors, calls dropped) during the study period. By characterizing, and if possible, addressing the limitations of our study, we will provide critical information for the feasibility of scaling up reminders and/or incentives to the regional or national levels in low-resource settings such as Tanzania.

With the continuing diffusion of mobile phones and the ongoing development of mHealth technologies, adaptive programming in the form of dynamic reminder systems and variable incentive structures has become a feasible reality even in low-resource settings. Our study sheds light on the demand-side barriers to vaccinations and the synergistic potential of combining mHealth reminders and incentives for improving vaccination coverage and timeliness. The results have implications for the design and potential efficacy of other subsidy or incentive programs aimed at improving health and health seeking behaviors.

References

1. World Health Organization. *Immunization coverage*. 2016 September 2016 [cited 2016 November 07]; Available from: <http://www.who.int/mediacentre/factsheets/fs378/en/>.
2. World Health Organization, *Global Vaccine Action Plan 2011-2020*. 2013, World Health Organization: Geneva, Switzerland.
3. Global Immunization Division, Centers of Disease Control and Prevention, and World Health Organization, *Epidemiology of the unimmunized child: Findings from the peer-reviewed published literature, 1999-2009*. 2009.
4. World Health Organization. *Immunization, Vaccines and Biologicals*. 2017 [cited 2017 October 26]; Available from: <http://www.who.int/immunization/en/>.
5. The DHS Program. *Demographic and Health Survey, and Malaria Indicator Survey, Tanzania*. 2015-16 [cited 2017 June 09]; Available from: <https://dhsprogram.com/pubs/pdf/FR321/FR321.pdf>.

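### Coverage has no time limit, so a comparison by assigned arm at end-line gives control events longer follow-up and counts control doses given after roll-over

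*Protocol*

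**What the plan says.** The protocol (Outcome measures) names coverage as the secondary outcome: "Secondary outcomes include vaccination coverage, in aggregate and for each of the vaccinations due at 6, 10 and 14 weeks after birth". The two outcome definitions stand next to each other. For timeliness: "Timeliness is defined as vaccination within 28 days of the scheduled vaccination due date". For coverage: "Coverage is defined as the percentage of children vaccinated". Only the first has a time limit.

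On arms, the protocol (Assignment to study arms and transitions between arms) says: "Assignment to study arms is implemented at the level of the vaccination event". Each event takes the arm of the phase in which it falls due. At T_2, "the beginning of Phase 2, all participants are rolled over to the arm with reminders"; at T_3, "all participants are rolled over to the arm with reminders combined with incentives". The same section says that one child's events can fall in different arms.

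The only practical end of observation is in Study activities: "An in-person end-line survey, conducted 12 months after enrollment", at which dates are taken from the government vaccination cards. The text does not name this survey as the cut-off for coverage. The SAP models on-time vaccination only and does not mention coverage.

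**The concern.** In this design calendar time separates the arms, and nobody stays in the control condition until end-line. An outcome without a time limit is therefore not observed on equal terms.

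- **Unequal follow-up.** Arm 1 events fall due earlier, so more weeks remain before the card review in which a late dose can be given.
- **Roll-over.** A control dose missed in Phase 1 may be given after T_2 or T_3, when the mother is receiving reminders or incentive offers for later visits. Under assignment by original scheduled date it still counts as vaccinated in arm 1. The same applies to arm 2 doses given after T_3.
- **Unit.** Aggregate coverage counted per child has no single arm when that child's three events span arms.

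At stake is the reading of the named secondary outcome. A null coverage result could reflect how the outcome was counted and not what the interventions did.

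**Working it through.** **Plan's own figure.** None is given for coverage. The stated power of 72% (98%) concerns timeliness and does not bear on this point.

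**Follow-up time.** Enrollment is in the third trimester and end-line is 12 months later (protocol). Assume birth 0-13 weeks after enrollment.

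- Child's age at end-line: 52 - 13 = 39 to 52 - 0 = 52 weeks.
- Time after the 6-week due date: 33 to 46 weeks.
- Time after the 14-week due date: 25 to 38 weeks.
- The timeliness window is 4 weeks.

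**Model for unequal follow-up.** Inputs from the protocol (Statistical power): on-time rates p of 65%, 75% and 80% (65% plus 10 and 15 points). Assumptions: typical due ages of 6, 10 and 14 weeks in arms 1, 2 and 3; end-line at child age 46 weeks; and a constant weekly catch-up rate h after day 28, the same in every arm and period.

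Coverage = p + (1 - p) × (1 - (1 - h)^w), with w = 46 - due age - 4, which is 36, 32 and 28 weeks.

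Example at h = 2%, arm 1: 0.98^36 = 0.483, so coverage = 0.65 + 0.35 × 0.517 = 83.1%.

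The reference is the same model with w = 36 weeks in all arms. The bias from unequal follow-up is the gap between the two sets of differences.

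| h per week | Coverage, arms 1/2/3 (%) | Difference from arm 1, arms 2/3 (points) | Same, equal 36 weeks | Lowered by |
|---|---|---|---|---|
| 2% | 83.1 / 86.9 / 88.6 | 3.8 / 5.5 | 4.8 / 7.2 | 1.0 / 1.7 |
| 5% | 94.5 / 95.2 / 95.2 | 0.7 / 0.8 | 1.6 / 2.4 | 0.9 / 1.6 |
| 10% | 99.2 / 99.1 / 99.0 | -0.1 / -0.3 | 0.2 / 0.3 | 0.3 / 0.6 |

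With 28 weeks for everyone as the reference, the lowering is 0.6-3.0 points.

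**No true effect.** Set p = 65% in every arm. Arm 1 minus arm 3 = 0.35 × ((1 - h)^28 - (1 - h)^36):

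- h = 2%: 0.35 × (0.568 - 0.483) = 3.0 points.
- h = 5%: 0.35 × (0.238 - 0.158) = 2.8 points.
- h = 10%: 0.35 × (0.052 - 0.023) = 1.0 point.

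**Is the 6/10/14-week mapping decisive?** A simulation replaced it with births uniform over 0-13 weeks after enrollment, enrollment spread over 0, 8 or 17 weeks (assumed), and T_2 and T_3 set for equal events per arm, as the protocol intends. Follow-up after day 28 averaged 35-37 weeks in arm 1 and 26-28 in arm 3. The no-effect gap was about 3-4 points at 2-5% per week. The conclusion does not rest on the mapping.

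**Roll-over.** The model has no catch-up caused by reminders or incentives. If C0 is control coverage without it and a share c of the missing control doses is given because of the later phases, observed control coverage rises by c × (1 - C0). The direction is toward no difference. The documents give neither C0 nor c.

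**Would a fixed window alone be enough?** Take 8 weeks as an example, with births even over 13 weeks. Due dates then run over weeks 6-19, 10-23 and 14-27. One third of events fall before T_2 = 14.33 weeks, since (8.33 + 4.33 + 0.33)/39 = 1/3. Control events whose window closes before T_2 are due before week 6.33, which is 0.33/13 = 2.6%, so about 97% of windows cross T_2. With births over 26 weeks, T_2 = 18.67 and (4.67 + 0.67)/26 = 20.5% close in time, so about 79% cross. A window equalises follow-up but does not remove roll-over.

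**The case against.** The strongest reply is that the plan specifies no arm comparison of coverage. The aim and hypothesis concern timeliness, and both analysis sections model on-time vaccination only. A reader might infer that the plan prescribes a wrong comparison. It does not: the comparison is left unstated. What remains is that a secondary outcome of a three-arm trial will be compared by arm, and the text offers only an open-ended definition for doing so.

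A reader might also infer that late control doses are certain to be credited to arm 1. That is the natural reading of assignment by scheduled date. However, the scheduling system shifts later due dates after a delay and reschedules reminders, so a missed dose might instead move to the arm of its new date, with a different bias. Incentives are paid only within 28 days of the due date, so a long-missed control dose would attract one only under a new due date, which again raises the question of its arm.

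A third tempting inference is that coverage is wholly per child and has no arm. Coverage is also reported for each vaccination, where each child has one event and an arm can be attached. Even the aggregate could mean pooled events. The unit problem is confined to an aggregate counted per child.

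Finally, the fall from 10 and 15 points for timeliness to the coverage differences in the table might be taken as the bias. Most of it is ordinary late vaccination, which coverage is meant to count, and it appears under equal follow-up too. The negative differences are 0.1-0.3 points at about 99% coverage, too little to support a claim that the result would reverse.

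**Conclusion.** The concern holds in a limited form. If coverage is read at end-line and compared by originally assigned arm, unequal follow-up and roll-over both pull the comparison toward no difference. At an assumed 2-10% weekly catch-up, unequal follow-up alone lowers the differences by about 0.3-1.7 points (36-week reference). With no true effect it favours arm 1 over arm 3 by about 3 points at 2-5% per week, and by about 1 point at 10%. Any extra catch-up caused by reminders or incentives would add to this and is not quantified.

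These figures illustrate and do not estimate: the documents give no coverage rate, catch-up rate, T_2 or T_3. The primary outcome has its own 28-day window and is not the subject here. The change should be made, but the point does not threaten the main analysis.

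**What to change.** In the protocol's Outcome measures and in the SAP:

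1. For the arm comparison, define coverage per vaccination event, as vaccinated within the same fixed number of days after the original due date in every arm.
2. State that the original scheduled date fixes the arm, even if the dose is rescheduled.
3. Add a sensitivity analysis that censors control doses at T_2 and arm 2 doses at T_3.
4. Report child-level completion of the three visits at end-line descriptively, without an arm comparison.

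The cost is a few sentences and one extra analysis, using dates already collected. The downside is that very late doses drop out of the arm comparison, and a short window brings coverage closer to timeliness.
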